#### **Secondary endpoints:**

A secondary endpoint will be to determine if the combination of the two agents can be associated with an increase in the disease-free survival (DFS) probability in patients with high grade NMIBC previously treated with BCG. If accrual is rapid, an amendment may be made to accrue additional patients to evaluate DFS as described in section [10.2](#).

A secondary objective is whether the combination is associated with changes in a set of immune parameters obtained from blood and biopsies.

A secondary objective is whether the pharmacokinetics of Vicineum can be determined from urine samples obtained within the first 7 days of Vicineum treatment.

A secondary objective is whether urinary EpCAM levels correlate with response to therapy.

A secondary objective is to assess PD-L1 expression and PD-1 expressing T cells in paired bladder biopsies pre- and post-treatment with durvalumab and Vicineum as a marker of response/benefit.

## **10.2 SAMPLE SIZE DETERMINATION**

The trial will begin with a 3-patient run-in at the proposed doses of Vicineum and durvalumab (1500mg; 30 mg) and if 0/3 or 1/3 patients have a DLT, then the next 3 patients will also be treated at the full doses of the agents (1500mg durvalumab; 30 mg Vicineum). If 0/6 or 1/6 has a DLT, then the remaining 18 patients will be treated at the full doses if the cumulative fraction of patients experiencing a DLT is <1/3.

If 2 or more patients among 3 to 6 have a DLT at 1500mg durvalumab and 30mg Vicineum, then 3 patients will be enrolled at the lower dose level (1500mg durvalumab and 20mg Vicineum), and if 0/3 or 1/3 patients have a DLT, then the next 3 patients will also be treated at the reduced doses of the agents. If 1/6 has a DLT, then the remaining patients will be treated at the lower dose level of the agents (1500mg durvalumab and 20mg Vicineum) if the cumulative fraction of patients experiencing a DLT is <1/3.

As the secondary endpoint, all the evaluable patients will have determinations of many immune parameters at baseline, 3 months, and 6 months. The changes in the parameters obtained from blood samples will be determined at baseline vs. 3 months, and baseline vs. 6 months. The changes in the parameters obtained from biopsies will be obtained from baseline vs. a single second biopsy at 6 months. A very large number of parameters may be evaluated, and unless more parameters than anticipated are to be evaluated, we will assume that 24 patients will be adequate to evaluate changes in these parameters based on the following. As an illustration, we will assume that a total of 25 paired tests will be considered of equal, primary importance. Paired results from 24 evaluable patients, including those used in the initial run-in portion who are treated at the highest safe dose, will provide 90% power to detect a change from baseline of 1.0 SD of the change (effect size=1.0) using a two-sided 0.002 significance level paired t-test, to allow an overall 0.05 significance level test, applying a very conservative Bonferroni adjustment to the set of approximately 25 paired comparisons. In practice, comparisons of the paired values will likely be performed using a Wilcoxon signed rank test instead of a paired t-test, and a Hochberg adjustment may be used instead of an overly stringent Bonferroni adjustment.

If accrual is sufficiently rapid, that is, if the 24 evaluable patients can be accrued within 2.5 years, then these 24 patients will be included in an expansion cohort, opened by an amendment to the study, designed to evaluate DFS, as follows that would allow for the enrollment of an additional 23 patients:

It has been estimated from published trials that the 6 month DFS in patients with high grade NMIBC previously treated with BCG is approximately 50%, and that it is 35% at 12 months, and 25% at 18 months. In this expansion cohort, the goal is to determine if use of a combination of Vicineum and durvalumab can be potentially associated with a 50% 1-year DFS probability. With 47 evaluable patients receiving the proposed therapy, including those in the initial 6 patients at the intended dose level as well as those in the evaluation of biologic endpoints, assuming accrual would take place over approximately 4 years, and that there would be at least 2 years of additional potential follow-up after the last patient has begun the therapy, there would be 80% power to determine whether there is a difference between a 35% 1 year DFS and an

improved 50% 1-year DFS, with a one sided 0.10 alpha level test, using the method of Brookmeyer and Crowley. In practice, Kaplan-Meier curves and appropriate confidence intervals at selected time points will be provided to help interpret results relative to the expected results.

It is anticipated that one patient per month may enroll onto this trial; thus, allowing for 6 to 12 separate patients as a run-in if needed, and 24 evaluable patients at the intended dose level, approximately 24-30 months would be the approximate accrual duration for the secondary endpoint based on evaluating biologic correlates. To allow for a small number of invaluable patients, the accrual ceiling will be set at 40. If the expansion to evaluate DFS will be undertaken, this will be modified by an amendment.

### **10.3 POPULATIONS FOR ANALYSIS**

Modified intention to treat: all patients who receive at least one dose of the two drugs will be included in the statistical analyses performed.

### **10.4 STATISTICAL ANALYSES**

#### **10.4.1 General Approach**

For the toxicity evaluation, the fraction of patients with toxicity will be determined and reported at each of the dose levels explored. The immune parameters will be obtained at baseline, 3 months, and 6 months and for each parameter, the change between baseline and the later time points will be calculated and evaluated for the statistical significance of the change. If the disease-free survival (DFS) is evaluated, a Kaplan-Meier curve for DFS will be constructed.

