We would like to continue the drug-combination trial since our preliminary interim data analysis shows a 40% 12 week response rate (5/12 patients) with half of them showing a  $>12$  month sustained response. We hypothesize that the prolonged response might be related to the systemic therapy (Durvalumab) administration. Also, most of the treatment related AEs are irritative voiding symptoms and most of them are grade 3 or lower, suggesting that the treatment is tolerated well thus far. Combination Therapy Dose Justification

In the single-agent phase I Vicineum study, there were no dose-limiting toxicities (DLTs) and no MTD was determined. Only 2 subjects of 64 had detectable plasma Vicineum levels and these were very near the lower level of quantitation. Durvalumab has been extensively studied in Phase I and Phase II and the recommended dose and safety profile has been established. For these reasons, the initial dose level for the combination will be the standard doses for both drugs. The FDA approved dose for durvalumab is currently 10mg/kg every 2 weeks and this amounts to 750 mg every 2 weeks for an average 75 kg individual. Based on pre-clinical data, there is no difference in exposure between weight based Q2W dosing and fixed dose Q4W dosing. Therefore, we are administering 1500 mg every 4 weeks instead of 750 mg every 2 weeks for ease and dosing convenience.

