##### **3.1.1 Dose Limiting Toxicity (DLT)**

A DLT will be defined as any Grade 3 or higher toxicity that occurs during the initial 6-week period the subject is on treatment (i.e., the DLT evaluation period). Toxicity that is clearly and directly related to the primary disease or to another etiology is excluded from this definition. Since this trial also involves immunotherapy, immune-related AEs (irAEs) are defined as AEs of an immune nature (i.e. inflammatory) in the absence of a clear alternative etiology. In the absence of a clinically significant abnormality, repeat laboratory testing will be conducted to confirm significant laboratory findings prior to designation as a DLT. The following will be DLTs:

- Inability to reduce prednisone dose below 10 mg within 6 weeks (rather than 12 weeks) due to ongoing immune-related adverse reaction of Grade >1
- Any Grade 4 irAE not attributed to local tumor response (e.g., inflammatory reaction attributed to local tumor response or inflammatory reaction at sites of metastatic disease or lymph nodes)
- Any  $\geq$  Grade 3 colitis
- Any Grade encephalopathy
- Any  $\geq$  Grade 3 neurotoxicity
- Any  $\geq$  Grade 3 peripheral neuromotor syndromes
- Any Grade 2 or higher noninfectious pneumonitis irrespective of duration
- Any Grade 3 irAE, excluding colitis that does not downgrade to Grade 2 within 3 days after onset of the event despite optimal medical management including systemic corticosteroids or does not downgrade to  $\leq$  Grade 1 or baseline within 14 days

- Total bilirubin  $>1.5 - 3.0 \times$  ULN (Grade 2 Hyperbilirubinemia)
- ALT or AST  $>8 \times$  ULN
- ALT or AST  $>5 \times$  ULN for more than 2 weeks
- ALT or AST  $>3 \times$  ULN and
- ALT or AST  $>3 \times$  ULN and INR  $>1.5$
- ALT or AST  $>3 \times$  ULN with appearance of fatigue, nausea, vomiting, right upper quadrant pain or tenderness, fever, rash, and/or eosinophilia ( $>5\%$ )
- Any Grade  $\geq 3$  non-irAE toxicity that does not downgrade to Grade  $\leq 1$  or baseline status (for patients who entered the study with an existing laboratory abnormality) within 14 days
- Inability to receive  $\geq 75\%$  or more of scheduled study treatment (both Vicineum and durvalumab) during the first six weeks of the trial

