- Sponsor or Manufacturer terminates the study
- The FDA requests that the sponsor terminate treatment of a specific subject or subjects or all subjects
- Subject noncompliance that, in the opinion of the investigator or sponsor, warrants withdrawal; e.g. refusal to adhere to scheduled visits
- Investigator discretion
- Positive pregnancy test or intent to become pregnant or intent to breast-feed or is breastfeeding
- Disease recurrence with high-grade bladder cancer

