## **8.2 ASSESSMENT OF SAFETY EVENTS**

AE information collected will include event description, date of onset, assessment of severity and relationship to study product and alternate etiology (if not related to study product), date of resolution of the event, seriousness and outcome. The assessment of severity and relationship to the study product will be done only by those with the training and authority to make a diagnosis and listed on the Form FDA 1572 as the site principal investigator or sub-investigator. AEs occurring during the collection and reporting period will be documented appropriately regardless of relationship. AEs will be followed through resolution.

SAEs will be:

- Assessed for severity and relationship to study product and alternate etiology (if not related to study product) by a licensed study physician listed on the Form FDA 1572 as the site principal investigator or sub-investigator.
- Recorded on the appropriate SAE report form, the medical record and captured in the clinical database.
- Followed through resolution by a licensed study physician listed on the Form FDA 1572 as the site principal investigator or sub-investigator.

For timeframe of recording adverse events, please refer to section [6.1](#). All serious adverse events recorded from the time of first investigational product administration must be reported to the sponsor.

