## 10 STATISTICAL CONSIDERATIONS

### 10.1 STATISTICAL HYPOTHESES

#### **Primary endpoints:**

The primary objective of this trial is to determine whether the use of a combination of Vicineum and durvalumab in patients with high grade NMIBC previously treated with BCG is safe and tolerable as determined by a 3+3 dose de-escalation trial design. The primary endpoint will be the fraction of patients who have adverse events.

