#### **10.4.2 Analysis of the Primary Endpoint**

All patients will be evaluated for the grades of toxicity identified, and the number of patients will DLTs at each dose level will be reported. The MTD will be identified based on being the dose level at which 0 or 1 patient in 6 has a DLT. All toxicities will be tabulated for all 24 or more patients to be enrolled onto the trial.

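### The crude toxicity fraction ignores time on treatment, so toxicity arising only with continued treatment is diluted: by up to about 1.3- to 2.6-fold for maintenance and about 3- to 6-fold for year 2.

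*Combined protocol and SAP*

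**What the plan says.** Safety and tolerability of the combination is the only primary objective (section 1.1.1). Section 10.1 defines the endpoint: "The primary endpoint will be the fraction of patients who have adverse events". It gives no time window or exposure basis. Section 10.3 sets the population: "all patients who receive at least one dose of the two drugs will be included in the statistical analyses performed". Section 10.4.1 reports toxicity by dose level only ("For the toxicity evaluation, the fraction of patients with toxicity will be determined and reported at each of the dose levels explored"), and section 10.4.2 adds: "All toxicities will be tabulated for all 24 or more patients to be enrolled onto the trial". Section 10.4.4 repeats this in substance.

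One toxicity measure has a fixed window. A DLT is "any Grade 3 or higher toxicity that occurs during the initial 6-week period the subject is on treatment" (section 3.1.1), with further qualifying and excluded events listed there. DLT counts by dose level and the MTD rule rest on it.

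Time on treatment is not fixed. The Précis and section 3.2 describe 12 weeks of induction, maintenance to 12 months, and an optional second year for patients still free of high-grade disease. Section 3.6.1 ends treatment for, among other reasons, "Disease recurrence with high-grade bladder cancer". Section 6.1 collects adverse events until 90 days after the last dose, and afterwards only those that are serious and related. Section 8.2 records timing: "AE information collected will include event description, date of onset". Section 10.4 plans no analysis of adverse events by period, per unit of exposure or as time to event, and section 10.4.8 rules out individual participant tabulations.

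**The concern.** The regimen under test is a maintenance regimen, so tolerability includes how it is borne by a patient who stays on it. A proportion over all treated patients mixes those who had one induction course with those treated for a year or two. Efficacy largely decides who is in which group. If a toxicity appears only with continued treatment, its few cases are divided by many patients who never had that treatment. With no events, the crude table also suggests more reassurance than the exposed patients can give.

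The DLT count does not fill the gap. By the study calendar (section 3.4) durvalumab is due in weeks 2, 6 and 10, so the 6-week window holds at most two doses. Without individual listings, a reader could not rebuild the late risk from the report.

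**Working it through.** **Reproducing the documents' figure.** Section 1.2.3 reports a "40% 12 week response rate (5/12 patients) with half of them showing a" response lasting more than 12 months. 5/12 = 41.7%, which agrees with the rounded 40%.

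**Formula.** Let s be the share of treated patients who enter a period and r the risk, among them, of an event that arises only there. The crude fraction is s × r, so it understates r by the factor 1/s. The factor does not depend on the sample size. Counts below use 24 patients at one dose level.

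**Inputs and results.** Response or disease-free status stands in for remaining on treatment.

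| Source | s, maintenance (about 3 months) | Of 24 | 1/s | s, year 2 (12 months) | Of 24 | 1/s |
|---|---|---|---|---|---|---|
| Interim data, section 1.2.3 | 5/12 = 41.7% | 10 | 2.4 | 2.5/12 = 20.8% | 5 | 4.8 |
| Vicineum phase 3 update, end of section 1.2.2 | 39% to 40% | 9.4 to 9.6 | 2.6 to 2.5 | 0.39 × 0.42 = 16.4% to 0.40 × 0.42 = 16.8% | 3.9 to 4.0 | 6.1 to 6.0 |
| Vicineum phase 2, section 1.2.2.2 | 20/45 = 44.4% | 10.7 | 2.25 | 7/45 = 15.6% | 3.7 | 6.4 |
| Historical DFS, section 10.2 (50% at 6 months, 35% at 12) | 71% to 75%, interpolated | 17 to 18 | 1.4 to 1.3 | 35% | 8.4 | 2.9 |
| DFS target, section 10.2 | not given | – | – | 50% | 12 | 2.0 |

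The interpolation to 3 months is an assumption. A constant hazard gives √0.50 = 70.7%, and a straight line gives (100% + 50%)/2 = 75%. Half of 5 is not a whole number of patients: 2/12 or 3/12 would give a year-2 factor of 6.0 or 4.0, inside the range shown.

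**What this does to a reported rate.** Take r = 20% for illustration.
- Maintenance: 0.20 × 0.417 = 8.3% on the interim figures; 0.20 × 0.707 = 14.1% to 0.20 × 0.75 = 15.0% on the DFS figures.
- Year 2: 0.20 × 0.208 = 4.2% on the interim figures; 0.20 × 0.35 = 7.0% on the DFS figures; 0.20 × 0.50 = 10.0% at the target.

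**Precision.**
- With no events, the one-sided 95% upper bound is 1 − 0.05^(1/n): 11.7% for n = 24, 25.9% for n = 10 and 45.1% for n = 5.
- One event gives 1/24 = 4.2% (exact 95% CI 0.1% to 21.1%) against 1/5 = 20% (0.5% to 71.6%).

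**The case against.** The crude fraction is not an error. It estimates the risk per patient who starts the regimen. Risk among those entering a later period is a different quantity, conditional on having tolerated and benefited from what came before. That stands, and it is why the crude table should stay.

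Patients who stop are still observed. Someone whose last dose is in week 12 is followed to about week 25 (90 days is about 13 weeks), which covers most of Maintenance #1 (weeks 15 to 27). Having had durvalumab, that patient is properly at risk of delayed immune events. The documents name no event confined to maintenance or year 2. The factors are therefore ceilings for a given share reaching the period, not estimates.

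A reader might infer that most patients leave at about 3 months and that maintenance toxicity is also diluted several-fold. The documents do not support this. It rests on 5/12, whose exact 95% CI is 15% to 72% (about 4 to 17 of 24), whereas section 10.2 takes DFS to be 50% at 6 months. It also treats every 12-week non-responder as stopping. Section 3.6.1 names high-grade recurrence, progression or no longer benefiting, and section 3.3.2 keeps patients with low-grade recurrence on trial. The phase 2 and phase 3 response rates come from patients with CIS, while this trial also enrols papillary disease.

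Nor is it right that event timing goes unused: the DLT definition depends on it. Finally, 1/24 and 1/5 have largely overlapping intervals, so the added table will show uncertainty more than it resolves it. That is true, but the uncertainty is what a reader needs to see.

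**Conclusion.** The point holds as a gap in the safety description. Beyond the 6-week DLT count, every planned toxicity summary is a proportion of all treated patients that takes no account of time on treatment. On the documents' figures, toxicity needing continued treatment could be understated by up to about 1.3- to 2.6-fold for maintenance and about 3- to 6-fold for year 2, or 2-fold if the DFS target is met. Several-fold is thus fair only for the optional second year.

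The sizes assume that response or freedom from disease stands in for being on treatment, that the 3-month DFS can be interpolated, and that the event occurs only in patients still treated. The documents do not give the number of patients who actually stopped, or how many eligible patients take up the second year. The DLT counts and the MTD rule are unaffected. This is a cheap improvement, not a flaw in the trial's decision rule.

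**What to change.** In sections 10.4.2 and 10.4.4, keep the crude tabulation by dose level and add a table of patients with events by period of onset:
- weeks 1–6
- weeks 7–12
- maintenance 1–3
- optional maintenance 4–7
- the 90-day follow-up after the last dose

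For each period give the number of patients who entered it as the denominator, the patient-months at risk and an exact 95% confidence interval. State which row takes the evaluation weeks 13 and 14. Count events after the last dose in the follow-up row. Base any statement about long-term tolerability on this table.

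A cumulative incidence curve for Grade ≥3 related events and immune-mediated AESIs is optional. If it is reported only to 12 months it says nothing about year 2, so it cannot replace the table.

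The cost is a few lines in the statistical section and some programming on onset dates already collected and the dosing records. No extra visits, patients or changes to treatment rules are needed. The downside is that late-period intervals will be wide and look less favourable.

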#### **10.4.2 Analysis of the Primary Endpoint**

All patients will be evaluated for the grades of toxicity identified, and the number of patients will DLTs at each dose level will be reported. The MTD will be identified based on being the dose level at which 0 or 1 patient in 6 has a DLT. All toxicities will be tabulated for all 24 or more patients to be enrolled onto the trial.

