#### Arms

Number	Name	Description
1	Run In	Durvalumab + Vicineum, escalating doses. Up to 2 dose levels will be evaluated in the first 6 – 12 subjects
2	Expansion	Durvalumab + Vicineum, at the MTD. Up to 24 subjects

Subjects in cohort 1 will be directly assigned to arm 1. Subjects in cohort 2 will be directly assigned to arm 2.

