### **3.1.2 Dose De-Escalation / Cohort Expansion**

- This trial will begin with a fixed dose of Vicineum 30 mg intravesical (Dose Level 1) administered once weekly for the first 12 weeks. Durvalumab administration will begin after 1 week of Vicineum monotherapy, at 1500mg IV once every 4 weeks.
- In the initial six patients, three subjects at a time will enroll at these doses and schedules (Dose Level 1). Dose-limiting toxicity (DLT) for each subject will be determined during the initial 6-week period that the subject is on treatment (i.e., the DLT period). When all subjects in the initial cohort have been on treatment through the DLT period, all available safety data will be considered in the decision to enroll additional subjects at this dose level, or to de-escalate the doses of the study drugs to Dose Level -1, based on a standard “3 + 3” design (see table below). There will be no dose-escalations in this study.

- After the first six to twelve patients, an additional 18 subjects will be enrolled at the highest dose level at which fewer than 2 of 6 subjects experienced DLT in order to obtain additional safety data and preliminary anti-tumor activity. Treatment at this level will continue as long as the cumulative fraction of patients experiencing DLT is < 1/3.

Dose De-Escalation Schedule	
Dose Level	Dose of IND Agent
Level 1	

• Durvalumab 1500mg IV every 4 weeks

• Vicineum 30 mg intravesically per dose*

Level -1	

• Durvalumab 1500mg IV every 4 weeks

• Vicineum 20 mg intravesically per dose*

\* Vicineum administered weekly during the first 12 weeks of the study, then every 2 weeks thereafter.

Dose de-escalation will follow the rules outlined in the Table below.

If 2 or more DLTs occur at dose level -1, then accrual to the trial will end pending an amendment to consider other dosing options to explore for safety before proceeding to explore efficacy.

Number of Patients with DLT at a Given Dose Level	De-Escalation Decision Rule
0 out of 3	Enter an additional 3 patients at same dose level
1 of 3	

Enter an additional 3 patients at Dose Level 1

• If 0 of these 3 patients experience DLT, enter additional patients at Dose Level 1

• If 1 or more of this group suffer DLT then enter up to 3 patients at the next lowest dose level. Reduce by 1

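### The MTD rule in sections 10.4.2 and 10.4.4 labels Level 1 the MTD if it passes, although a de-escalation-only design then supports only a tolerated level, with the MTD not reached

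*Combined protocol and SAP*

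**What the plan says.** Section 10.4.2, on the primary endpoint, gives the rule: "The MTD will be identified based on being the dose level at which 0 or 1 patient in 6 has a DLT". Section 10.4.4 repeats it. Neither section requires that a higher level was tested and failed, and neither says what is reported if the MTD is not reached. The Arms table in section 2.3.1 describes the expansion arm as "Durvalumab + Vicineum, at the MTD" and describes the run-in arm as having escalating doses.

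The design sections read differently. Section 10.1 says safety and tolerability are judged "as determined by a 3+3 dose de-escalation trial design". Section 3.1.2 states that "There will be no dose-escalations in this study", and the Design part of the précis says the same. The dose table in section 3.1.2 has two rows: Level 1, the starting level, with Vicineum 30 mg, and Level -1, with "Vicineum 20 mg intravesically per dose". Durvalumab is 1500 mg in both. Section 10.2 says what follows if Level 1 passes: "If 0/6 or 1/6 has a DLT, then the remaining 18 patients will be treated at the full doses", subject to the cumulative DLT fraction staying below 1/3.

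**The concern.** A maximum tolerated dose is a statement about a boundary: the named level is tolerated and the next one up is not. A design that starts at its top level and only moves down can support such a statement in one case, when the top level fails and the level below passes. When the top level passes, the trial has observed one level and knows nothing about anything above it. The rule in section 10 does not separate the two cases and gives both the same label.

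At stake is how the dose result is reported and read. A later trial that takes the label at face value could assume that a ceiling had been located when none was looked for.

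**Working it through.** **Does the design ever test above Level 1?** The plan states no figure for the behaviour of the MTD rule, so there is nothing to reproduce. The check is one of design logic.

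1. Levels available (section 3.1.2): Level 1 and Level -1 only.
2. Direction of movement (précis, sections 3.1.2 and 10.1): downward only.
3. If Level 1 has 0/6 or 1/6 DLTs, section 10.2 sends the remaining 18 patients to the same level. Level -1 is not opened.
4. If Level 1 has two or more DLTs among 3 to 6 patients, Level -1 opens.

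The possible results are therefore:

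| Level 1 | Level -1 | Label under 10.4.2 | What the data show |
|---|---|---|---|
| 0 or 1 DLT in 6 | not opened | Level 1 is the MTD | Level 1 met the rule; nothing above it studied |
| 2 or more DLTs | 0 or 1 DLT in 6 | Level -1 is the MTD | Level -1 met the rule and the level above failed |
| 2 or more DLTs | 2 or more DLTs | none | no tested level met the rule |

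The label is supported in the second row and unsupported in the first.

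**The protocol's own usage.** The dose justification text at the end of section 1.2.3 says of the single-agent Vicineum phase 1 study that "there were no dose-limiting toxicities (DLTs) and no MTD was determined". Section 1.2.2.2 shows that this study went up to 30.16 mg in 64 subjects. By that usage, 0/6 at Level 1 here would also give no MTD, yet section 10.4.2 would report one.

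**How likely is the first row?** Level 1 passes if at most one DLT occurs in two groups of three. With true DLT rate p:

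P(pass) = P(0/3) × [P(0/3) + P(1/3)] + P(1/3) × P(0/3) = (1−p)^6 + 6p(1−p)^5

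For p = 0.10: P(0/3) = 0.729 and P(1/3) = 0.243, so 0.729 × 0.972 + 0.243 × 0.729 = 0.7086 + 0.1771 = 0.886.

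| Assumed true DLT rate | P(Level 1 passes) |
|---|---|
| 5% | 0.967 |
| 10% | 0.886 |
| 15% | 0.776 |
| 20% | 0.655 |
| 25% | 0.534 |
| 30% | 0.420 |

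These rates are assumptions, because the documents give none.

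**Precision.** Exact (Clopper-Pearson) two-sided 95% intervals are 0 to 45.9% for 0/6 and 0.4% to 64.1% for 1/6. If the 18 expansion patients are counted at the same level, the denominator is 6 + 18 = 24. With 0/24, for example, the upper limit would be 1 − 0.025^(1/24), about 14%.

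**The case against.** The strongest reply is that nothing operational depends on the word. Section 3.1.2 sets the expansion dose by DLT count without mentioning an MTD, and section 10.2 does the same. That is right, and it limits the point to reporting.

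It can also be said that the plan defines its term, that some 3+3 plans loosely call the highest passing level the MTD, and that a reader who sees results by dose level and knows the design is de-escalation only will not be misled. This has some force, and harm to a careful reader is not certain. But the term is used differently in section 1.2.3, and the label would be quoted without the design around it. The section 1.2.3 comparison applies directly only to a result with no DLTs; for 1/6 the argument rests on the design logic alone.

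The pass probabilities do not measure an error. A starting dose with a low DLT rate ought to pass. They show only that the unsupported label would be used often. Likewise, the six-patient intervals describe precision and do not settle whether the label is right.

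Two stronger readings are tempting. A reader might infer that the dose statement is the main conclusion of the primary analysis. Section 10.1 names the fraction of patients with adverse events as the primary endpoint, and sections 10.4.1 and 10.4.2 also require toxicity and DLT counts by dose level. A reader might also infer that the rule is ambiguous because it does not specify the highest passing level. It is not: Level -1 opens only after Level 1 fails, so at most one level can meet it.

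**Conclusion.** The rule is wrong as written for the case where Level 1 passes. The supportable conclusion there is that the combination was tolerated, by the plan's criterion, at the highest level tested, and that the MTD was not reached. If Level 1 fails and Level -1 passes, the MTD label is defensible, for Vicineum at the fixed durvalumab dose.

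The effect is on the reported dose conclusion only. A reader might infer that enrolment, dosing, power or error rates are compromised; the documents do not support that, because none of them uses the label. The unsupported case is likely to arise: its probability is 97% to 66% at assumed true DLT rates of 5% to 20%. The logical point does not depend on those rates.

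The description of the run-in as escalating, in the Arms table, does not rescue the label. It contradicts the précis and section 3.1.2, and the dose table contains no level above the start.

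**What to change.** In sections 10.4.2 and 10.4.4, replace the MTD sentence with wording built on the rule already in section 3.1.2:

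- Report as the tolerated dose level the highest tested level with fewer than two DLTs among six patients.
- If that is Level 1, state that the MTD was not reached.
- Use the term MTD only if Level 1 fails and Level -1 passes.
- Report the DLT fraction at that level with an exact 95% interval over all DLT-evaluable patients treated there, including those in the expansion.

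In the Arms table, change the expansion description to match, and reconcile the escalating-dose description of the run-in with the statements in the précis and section 3.1.2 that there is no escalation.

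The cost is wording in three places and one added interval. No dose, cohort, sample size or data collection changes. The reported conclusion becomes slightly less strong.
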